In both cases, the null hypothesis (H_0) indicates that the means or medians of the 7 subpopulations are equal; the alternate hypothesis (H_a) refers to the above being different. If the p-value indicated by these tests is ≥ 0.05 (5%), it can be stated that there are no statistically significant differences between the means or medians of the 7 subpopulations, with 95% confidence, which is set for the investigation. If the p-value is < 0.05 , the hypothesis of equality of population means or medians (H_0) is rejected. This does not imply that a particular subgroup is superior or inferior to another.

For qualitative variables, a statistical test of the difference in proportions of the 7 subgroups (independent groups) will be performed by means of the Chi-square test. A result with a p-value ≥ 0.05 (5%) can be interpreted as: the proportions of the variable in question do not differ in terms of statistical significance, among the seven groups. In case the p-value is < 0.05 , it indicates that there are statistically significant differences between at least two of the seven groups with respect to the proportions of the variable been assessed. That does not imply that a particular subgroup is superior or inferior to another.

The results are shown in Table 4.

Specific Objective 3: To explore the acceptability of the topographic classification of

placenta accreta spectrum among obstetrician-gynecologists at the participating medical centers.

In the scientific literature there is no validated scale to evaluate the acceptability of a new clinical classification, which in this case is proposed as a topographic classification of PAS. After an exhaustive search, it was concluded that the *The Ottawa Acceptability of Decision Rules Instrument* would be utilized, which is a widely used instrument to evaluate the acceptability of a norm among physicians. There is no linguistic adaptation to Spanish, so a direct translation of its content was made.

After the principal investigator had reviewed it, was necessary make adaptations to some items, which were:

- a) Change the original term "norm" to "*anatomical classification for PAS*". In all items.

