- b) The following item is added: *The application of the anatomical classification for PAS generates an additional consumption of resources*. It is considered important to ask about that consideration, taking into account that the proposed classification will be very useful in low- and middle-income countries with limited healthcare systems.
- c) Item withdrawn: *The evidence supporting the norm is flawed*, as there are not enough studies addressing the present classification; therefore, it is not relevant to include the item.
- d) The following item is removed: *I am already following another norm or similar strategy*, since this proposed classification has no point of comparison with other types of classifications used in the day-to-day clinical practice.

Descriptive Analysis: Descriptive analysis will be performed using absolute frequencies and calculated percentages of the response option for each item. Finally, the absolute frequencies of each response option will be added up and the response percentage will be calculated to find the global acceptability of the anatomical classification of the placenta accreta spectrum, in relation to what was addressed in the survey.

The results are presented in Table 5.

Table of Variables

Variable Name	Definition	Type of variable	Operational Level	Measure Summary	Objective that resolves
1. Identifier number in the study	Unique consecutive number that identifies the participant in the study	Quantitative	Round numbers starting from 1	NA	NA
2. Date of surgery for PAS treatment	dd/mm/yyyy on which surgical management is performed for the treatment of placental accretism	NA	dd/mm/yy	NA	NA
3. Maternal age	Time in years, from the participant's date of birth to the date of visit, due to suspicion or diagnosis of PAS	Quantitative	Numbers greater ≥ 18	Central tendency and dispersion	1
4. Gravity	Number of pregnancies the patient has had at the time of the first visit for suspected or diagnosed PAS. (Considering the current pregnancy)	Quantitative	Number	Central tendency and dispersion	1
5. Parity	Number of previous deliveries of the patient at the first consultation for suspected or diagnosed PAS.	Quantitative	Number	Central tendency and dispersion	1
6. Previous Cesarean-sections	Number of previous cesarean sections the patient has had until the first visit for suspected or confirmed diagnosis of PAS	Quantitative	Number	Central tendency and dispersion	1

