Yes	n (%)	n (%)	n (%)	n (%)	n (%)	n (%)	n (%)	
Supra-fascial hematoma								
No	n (%)	n (%)	n (%)	n (%)	n (%)	n (%)	n (%)	
Yes	n (%)	n (%)	n (%)	n (%)	n (%)	n (%)	n (%)	
Surgical reintervention								
No	n (%)	n (%)	n (%)	n (%)	n (%)	n (%)	n (%)	
Yes	n (%)	n (%)	n (%)	n (%)	n (%)	n (%)	n (%)	
Maternal death								
No	n (%)	n (%)	n (%)	n (%)	n (%)	n (%)	n (%)	
Yes	n (%)	n (%)	n (%)	n (%)	n (%)	n (%)	n (%)	
Classification of complications								
Grade I	n (%)	n (%)	n (%)	n (%)	n (%)	n (%)	n (%)	
Grade II	n (%)	n (%)	n (%)	n (%)	n (%)	n (%)	n (%)	
Grade IIIa	n (%)	n (%)	n (%)	n (%)	n (%)	n (%)	n (%)	
Grade IIIb	n (%)	n (%)	n (%)	n (%)	n (%)	n (%)	n (%)	
Grade IVa	n (%)	n (%)	n (%)	n (%)	n (%)	n (%)	n (%)	
Grade IVb	n (%)	n (%)	n (%)	n (%)	n (%)	n (%)	n (%)	
Grade V	n (%)	n (%)	n (%)	n (%)	n (%)	n (%)	n (%)	

Table 5. Acceptability of the anatomical classification for placenta accreta spectrum among obstetrician-gynecologists from the participating medical centers (N).

Statements	Strongly disagree	Moderately disagree	Slightly Disagree	Slightly agree	Moderately agree	Totally agree	No opinion/ Don't know
The anatomical classification for PAS is easy to use.	n (%)	n (%)	n (%)	n (%)	n (%)	n (%)	n (%)
The anatomical classification for PAS is easy to remember.	n (%)	n (%)	n (%)	n (%)	n (%)	n (%)	n (%)
The anatomical classification for PAS is useful to me.	n (%)	n (%)	n (%)	n (%)	n (%)	n (%)	n (%)
The anatomical classification for PAS is clear and unambiguous.	n (%)	n (%)	n (%)	n (%)	n (%)	n (%)	n (%)

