My colleagues would support the use of anatomical classification for PAS.	n (%)	n (%)	n (%)	n (%)	n (%)	n (%)	n (%)
Patients would benefit from the use of anatomical classification for PAS.	n (%)	n (%)	n (%)	n (%)	n (%)	n (%)	n (%)
The use of anatomical classification for PAS would result in a better use of resources.	n (%)	n (%)	n (%)	n (%)	n (%)	n (%)	n (%)
The use of anatomical classification for PAS would increase the likelihood of lawsuits	n (%)	n (%)	n (%)	n (%)	n (%)	n (%)	n (%)

The anatomical classification for PAS does not take into account an important clinical detail	n (%)	n (%)	n (%)	n (%)	n (%)	n (%)	n (%)
The environment in which I work makes it difficult to use the anatomical classification for PAS.	n (%)	n (%)	n (%)	n (%)	n (%)	n (%)	n (%)
The application of topographic classification generates additional resource consumption.	n (%)	n (%)	n (%)	n (%)	n (%)	n (%)	n (%)
TOTAL	n (%)	n (%)	n (%)	n (%)	n (%)	n (%)	n (%)

OPERATIONAL ASPECTS

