forms. Once the participant accepts, they will be able to continue filling out the survey; if the participant does not accept, the surveys will be made not available to be completed (**Annex 2**).

- ***Request for waiver of informed consent***

As mentioned above, this study will only use data from the medical records of the participants and will not carry out any type of intervention nor will it imply changes in the clinical behavior or prognosis of the patients admitted, for which reason an exception to the informed consent will be requested from the ethics committee of Fundación Valle del Lili.

- ***Risk-control strategies***

One of the potential risks of this study is the identification of the participating patients, therefore, we are committed to maintaining strict confidentiality and will not publish images or anything that confirms patients are participating. In order to guarantee this, the patients will be hidden by means of numerical codes; furthermore, no person outside the research or the ethics committee will have access to the data. We declare that we are aware of and comply with the 1995 declaration of 1999 that regulates the use medical records in Colombia.

- ***Conflict of interest***

The researchers state that there are no conflicts of interest. This research has no direct impact on natural or environmental resources.

- ***Author***

The products of the proposed project will comply with the institutional rules of authorship, which in turn will be aligned with the recommendations of the ICMJE.

Activity/ Year/ Name of month	202 2 Oct	202 2 Nov	202 2 Dec	202 3 Jan	202 3 Feb	202 4 Jan	202 4 Feb	202 4 Mar	202 4 Apr	202 4 May
1. Writing the protocol	x	x								
Approvals										
2. Socializing the protocol			x							
3. Methodology Evaluation			x							
4. Ethics committee evaluation				x	x					
Execution										
5. Collecting of the information					x	x				
6. Analysis of the data							x			
Socialization of Results and Reports										
7. Writing the paper								x		
8. Poster presentation (if applicable)									x	
9. Article Submission										x
10. Reporting to Ethics Committee						x				
11. (Annual - Renewal)										

REFERENCES

1. [name] JM, Fiorillo A, Hamer J, Martínez M, Bruno C. Placenta accreta spectrum: a hysterectomy can be prevented in almost 80% of cases using a resective-reconstructive technique. *Journal of Maternal-Fetal and Neonatal Medicine*. 2022;35(2):275-82.

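### The global acceptability total in Table 5 adds up favourable and unfavourable survey items without reverse-coding, so it does not measure acceptance

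*Combined protocol and SAP*

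**What the plan says.** The analysis text for Specific Objective 3 has two steps. The first is by item: "Descriptive analysis will be performed using absolute frequencies and calculated percentages of the response option for each item". The second pools the items: "the absolute frequencies of each response option will be added up and the response percentage will be calculated to find the global acceptability". Table 5 shows the result as a single total row beneath 11 statements, with six columns running from disagreement to agreement and a seventh for no opinion.

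The statements point in two directions:

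- **Seven favour the classification:** ease of use ("The anatomical classification for PAS is easy to use"), ease of remembering, usefulness, clarity, support from colleagues, benefit to patients, and better use of resources.
- **Four speak against it:** "The use of anatomical classification for PAS would increase the likelihood of lawsuits"; "The anatomical classification for PAS does not take into account an important clinical detail"; "The environment in which I work makes it difficult to use the anatomical classification for PAS"; and a statement, added by the study team, that applying it consumes extra resources.

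The survey is adapted from a published acceptability instrument. The list introduced by "After the principal investigator had reviewed it, was necessary make adaptations to some items, which were" covers one change of term, one added item and two removed items. It does not touch scoring. The Table of Variables assigns its 25 entries to Objective 1, Objective 2 or neither, so it codes no survey item. Operational Aspects says the analysis will follow the variable and blank tables.

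**The concern.** Under this rule, strong agreement that the classification invites lawsuits is counted in the same column as strong agreement that it is easy to use. Because the items point both ways, no set of agree or disagree columns in the total row can stand for acceptance.

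The two resource items show this most plainly. A respondent who thinks the classification saves resources would naturally agree with one and disagree with the other. The total row then splits one favourable view between opposite columns.

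The Research Hypotheses section expects high acceptability among obstetrician-gynecologists, and the pooled row is the only planned overall figure that bears on it. Read in the natural way, with agreement as acceptance, that figure rises when respondents agree more with the objections.

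**Working it through.** The plan states no acceptability figure, survey size or threshold, so there is nothing to reproduce. The check applies the stated rule to constructed response patterns.

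**Inputs.** From Table 5: 7 favourable items, 4 unfavourable items, 11 in all. Two assumptions are mine: the three agree columns are read as acceptance, and there are no no-opinion answers.

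**Formulas.** Let a be the share of agree answers on the favourable items and b the share on the unfavourable items.

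- Planned total: T = (7a + 4b)/11
- Reverse-coded total: R = (7a + 4(1 − b))/11 = T + (4 − 8b)/11

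**Results.**

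| Pattern | a | b | Planned T | Reverse-coded R |
|---|---|---|---|---|
| Full acceptance | 1 | 0 | 7/11 = 63.6% | 11/11 = 100% |
| Full rejection | 0 | 1 | 4/11 = 36.4% | 0/11 = 0% |
| Agrees with everything | 1 | 1 | 11/11 = 100% | 7/11 = 63.6% |
| Mostly favourable | 0.9 | 0.1 | 6.7/11 = 60.9% | 9.9/11 = 90.0% |
| Lukewarm, with objections | 0.5 | 0.8 | 6.7/11 = 60.9% | 4.3/11 = 39.1% |
| Mostly unfavourable | 0.1 | 0.9 | 4.3/11 = 39.1% | 1.1/11 = 10.0% |

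**What a given total can mean.** For fixed T, b can lie between max(0, (11T − 7)/4) and min(1, 11T/4). Putting these limits into R gives:

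- T = 60.9%: b from 0 to 1, so R from 2.7/11 = 24.5% to 10.7/11 = 97.3%.
- T = 90%: b from 0.725 to 1, so R from 5.9/11 = 53.6% to 8.1/11 = 73.6%.
- T = 10%: b from 0 to 0.275, so R from 2.9/11 = 26.4% to 5.1/11 = 46.4%.

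These are mathematical bounds. Extreme totals carry some information; middling ones carry little.

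**Direction.** Any total above 7/11 = 63.6% requires some agreement with the objections. Each 10-point rise in b moves T up by 0.4/11 = 3.6 points and R down by the same amount. Since R − T = (4 − 8b)/11, the planned total understates acceptance when b is below 50% and overstates it when b is above 50%.

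**The case against.** **A scoring rule may exist elsewhere.** The Ethical Considerations section points to Annex 2 in connection with the survey, and that annex was not available for this check. The parent instrument may also have a scoring convention that was meant to carry over. Neither can be excluded. But the analysis section states a plain sum, so any such rule would have to be reconciled with it.

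**The plan never collapses the columns.** It reports a percentage for each response option and sets no cut-off for high acceptability, so the percentages above depend on my reading. That is true of the figures. The defect does not depend on that reading: each of the six columns already mixes favourable and unfavourable answers, and the plan still calls the result global acceptability.

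**The wide range is a bound.** Its low end at 60.9% needs agreement with every objection and only 2.7/7 = 38.6% agreement on the favourable items. Respondents will have applied the classification themselves, at centres experienced or trained in it, so this is improbable. If agreement with the objections is assumed to lie between 0% and 30%, a total of 60.9% means reverse-coded acceptance of 8.3/11 = 75.5% to 97.3%. In that region the planned total errs against the hypothesis. This stands, but it means near-unanimous acceptance would look lukewarm, which is still a wrong figure.

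**The consequence is small.** Objective 3 is exploratory and descriptive, with no test or sample size attached, and every item row is reported. A reader could rebuild a corrected total from Table 5. This stands too, and it limits the weight of the point.

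**Conclusion.** The concern holds and should be fixed. Followed as written, the plan produces an overall figure on which full acceptance shows 63.6% agreement, full rejection still shows 36.4%, and the maximum of 100% goes to respondents who also endorse every objection. Patterns with reverse-coded acceptance of 90.0% and 39.1% share the same total, 60.9%.

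These numbers assume that agreement is read as acceptance and that there are no no-opinion answers; they are illustrations, not forecasts. The absence of reverse-coding is established for the available text only.

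The damage is confined to the six agree/disagree columns of the total row and to any statement about global acceptability drawn from them. The item rows, the no-opinion column and Objectives 1 and 2 are unaffected.

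**What to change.** In the Specific Objective 3 analysis text, either reverse-code the four unfavourable items before pooling, or replace the single total with one total for the seven favourable items and one for the four unfavourable items. State which response options count as acceptance and how no-opinion answers enter the denominator. If Annex 2 holds a scoring key, make the analysis text agree with it. Keep the item rows and the no-opinion column of Table 5 as they are.

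The cost is one or two sentences and a recode of four items, or one extra row in Table 5. The questionnaire does not change and no new data are needed.

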In addition to the difficulties associated with the traditional classification, it does not provide an ideal route on how to manage each case. The management options for PAS are multiple (10,11), without concretely defining which strategy is superior to others. It is common for a hospital and its PAS expert group to choose one type of treatment option and specialize in it, applying it in almost all their cases despite the variability of clinical presentations of PAS. For example, some protocols include embolization before or after fetal extraction (12), others apply total (13) or subtotal (14) hysterectomy in all cases, and others prefer expectant management, leaving the placenta in situ and waiting for its expulsion or resorption after a few weeks (15).

The indiscriminated application of a specific procedure, exposes patients with less severe forms of PAS to the complications of that procedure (16), probably without gaining any additional benefit since they could have been managed with simpler interventions (2). Vascular management procedures (endovascular balloons, retroperitoneal dissection for aortic or internal iliac vessel clamping) have risks (17). Even total abdominal hysterectomy is associated with early ovarian failure and irreversible loss of fertility, along with psychological consequences for patients (18). Furthermore, it has been repeatedly demonstrated that hysterectomy is associated with greater blood loss, a higher rate of maternal complications and increased admission to intensive care for catastrophic bleeding (>2500 ml) compared to uterine sparing surgery (19).

Topographic classification

Due to the situation with the traditional classification, an interesting proposal rises, which is the topographic classification created by [name] et al (1). This classification considers which uterine wall is affected (anterior, posterior or lateral), in addition to the level of involvement of the uterus (above or below the vesicouterine peritoneal fold) (4).

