In both cases, the null hypothesis (H_0) indicates that the mean or median numbers of the 7 subpopulations are equal; the alternate hypothesis (H_a) refers to the above being different. If the p-value indicated by those tests is ≥ 0.05 (5%), it can be stated that there are no statistically significant differences between the mean or median numbers of the 7 subpopulations, with 95% confidence, which is set for the study. If the p-value is < 0.05 , the hypothesis of having no difference in the mean or median numbers (H_0) is rejected. That does not imply that a particular subgroup is superior or inferior to another.

For qualitative variables, a statistical test of the difference in proportions of the 7 subgroups (independent groups) will be performed by means of the Chi-square test. A result with a p-value ≥ 0.05 (5%) can be interpreted as: the proportions of the variable in question do not differ, in terms of statistical significance, among the seven groups. In case the p-value is < 0.05 indicates that there are statistically significant differences between at least two of the seven groups with respect to the proportions of the variable addressed. This does not imply that a particular subgroup is superior or inferior to another.

The results are shown in Table 3.

Specific Objective 2: To analyze the clinical outcomes of patients diagnosed with placenta accreta spectrum according to anatomical classification.

Descriptive Analysis: Stratification by subgroups will be performed according to the anatomical classification of PAD as follows: T1, T2a, T2b, T3, T4, T5a and T5b. Qualitative variables will be summarized as percentages and presented as absolute frequencies. For quantitative variables, the normality distribution will be determined by means of the Kolmogorov statistic.

Smirnov (sample size greater than 50 patients is expected), where a result of p-value >0.05 would comply with the assumption of normality. For variables with normal distribution, mean and standard deviation will be determined; and for variables without normal distribution, median and interquartile ranges (Q1 - Q3) will be indicated.

Inferential Analysis: For quantitative variables, a statistical test of the difference in means of the 7 subgroups (independent groups) will be performed by means of one-way ANOVA for independent groups. If the variable does not have a normal distribution, the Kruskal-Wallis test will be performed.

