7. Placenta previa in the current pregnancy	Is there placenta previa (total/partial/low lying) in the current pregnancy?	Qualitative Nominal	0: No 1: Yes	Central tendency and dispersion	1
8. Prenatal diagnostic method of PAS	Diagnostic imaging study by which PAS is diagnosed	Qualitative Nominal	1: Ultrasound 2: Magnetic Resonance Imaging 3: Ultrasound and Magnetic Resonance Imaging 4: PAS prenatal diagnosis not available	Absolute frequency and percentage	1

			(intraoperative diagnosis of PAS)		
9. Gestational age at the time of delivery	Weeks of gestation at time of delivery of the current pregnancy	Quantitative	Number	Central tendency and dispersion	1
10. Topographic classification ([name])	Classification into 7 groups as described in Annex 1	Qualitative Ordinal	1: Type 1 2: Type 2U 3: Type 2L 4: Type 3 5: Type 4 6: Type 5U 7: Type 5L	Frequencies and percentages	1
11. Days of postoperative hospitalization	Number of days the patient was hospitalized from the day of surgery to the day of discharge.	Quantitative	Number	Central tendency and dispersion	1
12. Surgical time	Time in minutes between skin incision to skin closure	Quantitative	Number	Central tendency and dispersion	1

CLINICAL OUTCOME VARIABLES					
13. Type of surgery	Type of surgical priority	Qualitative Nominal	0: Programmed 1: Emergent	Frequencies and percentages	2
14. Intervention performed	Treatment option used	Qualitative Nominal	0: Total hysterectomy 1: Modified subtotal hysterectomy 2: One step conservative surgery 3. Other	Frequencies and percentages	2
15. Criteria on how to select surgical technique	Criteria for the selection of the type of intervention applied as management	Qualitative Nominal	1: Surgical technique chosen based on the topographic classification 2: Surgical technique chosen without the topographic classification	Frequencies and percentages	2
16. Volume of intraoperative blood loss	Blood volume lost during surgery measured in (ml)	Quantitative	Number	Central tendency and dispersion	2
17. Usage of vascular interventions	What type of vascular intervention was used during the surgery	Qualitative Nominal	1: None 2: Ligation of internal iliac arteries 3: Endovascular occlusion of internal iliac or common iliac arteries (balloons) 4: Clamping or ligation of the aorta 5: Aortic Endovascular Occlusion (Balloon) 6: Manual aortic compression 7. Other	Frequencies and percentages	2

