Surgery one-step conservative	n (%)	n (%)	n (%)	n (%)	n (%)	n (%)	n (%)	
Vascular intervention	n (%)	n (%)	n (%)	n (%)	n (%)	n (%)	n (%)	
None	n (%)	n (%)	n (%)	n (%)	n (%)	n (%)	n (%)	
Ligation of internal iliac arteries	n (%)	n (%)	n (%)	n (%)	n (%)	n (%)	n (%)	
Endovascular occlusion of internal iliac or common iliac arteries (balloons)	n (%)	n (%)	n (%)	n (%)	n (%)	n (%)	n (%)	
Clamping or ligation of aorta	n (%)	n (%)	n (%)	n (%)	n (%)	n (%)	n (%)	
Endovascular aortic occlusion (Balloon)	n (%)	n (%)	n (%)	n (%)	n (%)	n (%)	n (%)	
Manual aortic compression	n (%)	n (%)	n (%)	n (%)	n (%)	n (%)	n (%)	
Another	n (%)	n (%)	n (%)	n (%)	n (%)	n (%)	n (%)	

--	--	--	--	--	--	--	--	--

Stage of Hemorrhage								
Stage 1	n (%)	n (%)	n (%)	n (%)	n (%)	n (%)	n (%)	
Stage 2	n (%)	n (%)	n (%)	n (%)	n (%)	n (%)	n (%)	
Stage 3	n (%)	n (%)	n (%)	n (%)	n (%)	n (%)	n (%)	
Stage 4	n (%)	n (%)	n (%)	n (%)	n (%)	n (%)	n (%)	
Stage 5	n (%)	n (%)	n (%)	n (%)	n (%)	n (%)	n (%)	
Bladder Injury								
No	n (%)	n (%)	n (%)	n (%)	n (%)	n (%)	n (%)	
Yes	n (%)	n (%)	n (%)	n (%)	n (%)	n (%)	n (%)	
Ureteral Injury								
No	n (%)	n (%)	n (%)	n (%)	n (%)	n (%)	n (%)	
Yes	n (%)	n (%)	n (%)	n (%)	n (%)	n (%)	n (%)	
Arterial Thrombosis								
No	n (%)	n (%)	n (%)	n (%)	n (%)	n (%)	n (%)	
Yes	n (%)	n (%)	n (%)	n (%)	n (%)	n (%)	n (%)	
Post-operative ileus								
No	n (%)	n (%)	n (%)	n (%)	n (%)	n (%)	n (%)	

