Subsequently, the methodology advisor and the statistical team will perform the analysis according to the tables of variables and blank tables proposed display the patients' characteristics and the results of the study. Once the above process has been completed, the manuscript will be written.

SOCIALIZATION OF RESULTS

The manuscript resulting from this study will be published in a journal indexed in Web of Science and/or SCOPUS; in addition, the results will be presented at congresses and other academic events related to the subject and the area of Obstetrics & Gynecology. The expected audience is obstetrician-gynecologists, as well as personnel in training in health areas, such as resident physicians and/or undergraduate students.

ETHICAL CONSIDERATIONS

The present study adheres to the Helsinki declaration and the 2016 CIOMS guidelines. All the investigators have successfully completed and passed the *Good Clinical Practice* (GCP) course, which is designed to prepare research personnel on how to conduct clinical trials with human participants.

Researchers agree to comply with the principles and responsibilities defined in the 2010 Singapore Declaration on Integrity in Research. All investigators state that they are aware

of the four principles of bioethics such as: autonomy, recognizing that all patients are capable of deliberating about their personal goals and acting on the decisions they can make. Patients with limited autonomy are entitled to protection. Beneficence, as the moral obligation to act in the welfare of others. Non-maleficence, which is understood as doing no harm and preventing harm. And justice, acting in an ethical and equitable manner.

- ***Risk Level (According to Resolution 8430)***

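### Table 4 has no row for blood loss in millilitres and shows an undefined five-level hemorrhage stage instead, in conflict with variable 16 and the Objective 2 analysis

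*Combined protocol and SAP*

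**What the plan says.** In the Table of Variables, variable 16 is intraoperative blood loss, defined as "Blood volume lost during surgery measured in (ml". It is typed as quantitative, summarised by a measure of centre and spread, and assigned to Objective 2.

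Under Data Management and Statistical Analysis, Specific Objective 2, quantitative outcomes get "a statistical test of the difference in means of the 7 subgroups (independent groups) will be performed by means of one-way ANOVA", with Kruskal-Wallis if the variable is not normal. Qualitative outcomes get "a statistical test of the difference in proportions of the 7 subgroups (independent groups) will be performed by means of the Chi-square test". The section closes with "The results are shown in Table 4".

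Table 4 in Blank Tables has seven columns of topographic types and a p-value column. Its only bleeding row is "Stage of Hemorrhage", with Stages 1 to 5 as counts and percentages. It has no row in millilitres.

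Operational Aspects says that the methodology advisor and statistical team "will perform the analysis according to the tables of variables and blank tables". Both tables are therefore binding.

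**The concern.** An analyst cannot satisfy both tables. The planned ANOVA or Kruskal-Wallis on blood loss has no row in the table that is meant to carry its result, and the bleeding row in that table has no variable behind it. No cut-points are given, so two analysts could fill the stage row differently from the same data.

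Blood loss matters here. The Topographic classification section names less bleeding in type 1, and more in the low parametrial and bladder-trigone types, among the retrospective findings, and the study is justified by the lack of prospective multicentre evidence on such associations. Variable 16 is the only listed variable that measures blood lost. If the blank table prevails, a continuous measure is replaced by an undefined grouping, and the plan's general rule sends that grouping to a test that ignores the order of the stages.

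**Working it through.** **1. The two instructions side by side.** Of the Objective 2 variables (13 to 25), only variable 16 is quantitative; the rest are nominal or ordinal. The ANOVA/Kruskal-Wallis paragraph for Objective 2 therefore applies to blood loss alone, yet Table 4 contains no quantitative row. None of variables 1 to 25 is a hemorrhage stage. Where the plan uses another graded scale it cites an annex: variable 10 cites Annex 1 and variable 25 cites Annex 3. Annex 2, which is not visible here, is cited for the physicians' survey. The only blood-loss threshold in the text is in the background ("increased admission to intensive care for catastrophic bleeding (>2500 ml"), and it is not tied to any stage.

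**2. The plan's own figure.** The plan states no power for blood loss. Its sample size concerns total complications, type 1 against type 4: p1 = 0.3105, p2 = 0.9999, two-sided 5%, 80% power, ratio 1. With d = 0.6894 and mean proportion 0.6552:
- Kelsey: (1.96 + 0.8416)² × 2 × 0.6552 × 0.3448 / d² = 7.46, rounded up to 8.
- Fleiss: [1.96√(2 × 0.6552 × 0.3448) + 0.8416√(0.3105 × 0.6895 + 0.9999 × 0.0001)]² / d² = 6.13, rounded up to 7.
- With continuity correction: (6.13/4) × [1 + √(1 + 4/(6.13 × d))]² = 8.79, rounded up to 9.

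These match the stated 8, 7 and 9 per group. They say nothing about bleeding; the useful input is the target of at least 9 patients in the rarest type.

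**3. Degrees of freedom.** Kruskal-Wallis on seven types: 7 − 1 = 6. Pearson chi-square on seven types by five stages: (7 − 1)(5 − 1) = 24. The 5% critical values are 12.59 and 36.42.

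**4. Power from the non-central chi-square.** Take the non-centrality that gives a chosen power at 6 df. Then compute power at 24 df with the same value, and with 0.9 of it (an assumed 10% information loss from grouping).

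| Power, 6 df | Non-centrality | Power, 24 df, same | Power, 24 df, 0.9 of it |
|---|---|---|---|
| 50% | 7.50 | 26.8% | 24.0% |
| 80% | 13.62 | 51.5% | 46.0% |
| 90% | 17.42 | 65.5% | 59.3% |
| 95% | 20.86 | 75.9% | 69.8% |

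**5. Simulation (600 runs per setting).** Assumptions, none from the documents: normal blood loss on a suitable scale, SD 1, shift graded across types.

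| Layout | Largest shift | Stage shares (%) | Kruskal-Wallis, ml | Chi-square, stages |
|---|---|---|---|---|
| 9 per type, N = 63 | 1.0 SD | 20 each | 39% | 20% |
| same | 1.0 SD | 50/25/15/7/3 | 42% | 16% |
| same | 1.5 SD | 20 each | 83% | 46% |
| same | 1.5 SD | 50/25/15/7/3 | 78% | 35% |
| Type 1 = 146, others 9, N = 200 | 0.8 SD | 20 each | 75% | 41% |
| same | 0.8 SD | 50/25/15/7/3 | 77% | 74% |

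The last row shows almost no loss, but in that setting the chi-square rejects a true null 8.0% of the time, so part of its apparent power is inflated error. A separate simulation with permutation p-values avoids this. With lognormal loss, log-SD 0.6, N = 200, type 1 = 146 and lower-level types 1.5-fold higher, it gave 69–77% on millilitres and 20–57% on stages, depending on the assumed median and cut-points. With a 2-fold difference it gave 100% against 77–99%.

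**6. Where the loss comes from.** With nine per type and even stages, Kruskal-Wallis on the ordered stages gives 38% against 39% on millilitres (1.0 SD) and 78% against 83% (1.5 SD). Grouping costs little; the nominal 24-df test costs most.

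**7. Sparse cells.** A type with 9 patients and even stages has 9 × 0.2 = 1.8 expected per cell. Across the layouts and stage shares tried, 74–100% of cells fall below 5, and the size of the chi-square runs from 2.5% to 9.6%.

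**The case against.** The strongest reply is that the millilitre analysis is already planned. Variable 16 and the Objective 2 text together specify it, and Operational Aspects puts the variable table alongside the blank tables. This stands. A reader might infer that the plan has switched its bleeding outcome to stages, or that no bleeding result could be reproduced. The documents do not support either: they hold an unresolved contradiction, and only the stage row is irreproducible.

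A reader might also infer that the stages would be cut from the millilitre data at limits chosen after seeing them. Nothing says the stage derives from variable 16. It may be a separate clinical staging or a leftover row. Other blank-table rows are out of step too: Table 3 has a trimester-of-diagnosis row with no variable, and shows previous cesareans as yes/no although the variable is a count.

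It is tempting to say that half the power is lost. That fits small or evenly staged groups at moderate power, but it is not a general figure. The chi-square on this row is itself an inference from the rule for qualitative variables and the p-value column. Nor does the plan rank any outcome as primary, so blood loss cannot be called its main result.

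None of this removes the missing millilitre row or the missing stage definition.

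**Conclusion.** The concern holds as a conflict between two governing tables. Blood loss is collected and analysed in millilitres by the text, but Table 4 omits it and shows a five-level stage that cannot be reproduced from the documents. This part rests on the documents alone.

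The effect on power is conditional on Table 4 being followed and the stage row being tested by the plan's chi-square rule. The 80% to 46.0–51.5% figure assumes equal or 10% lower non-centrality. Over the wider range the loss runs from almost none to more than half, according to group sizes, cut-points and effect, which the documents do not fix beyond the target of 9 in the rarest type. The point is worth correcting before analysis; it does not threaten the study as a whole.

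**What to change.** In Table 4, add blood loss in millilitres by topographic type, with median, interquartile range and a Kruskal-Wallis p-value, and name it as the bleeding result. This agrees with variable 16 and uses a test the Objective 2 text already provides.

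Then either delete the Stage 1 to 5 row, or keep it as a secondary row. If it is kept, add the stage to the Table of Variables, fix its source and cut-points before analysis, and test it as ordered, for example by Kruskal-Wallis on the stage number. An extra yes/no row at 2500 ml is not needed: that figure is background, not a study threshold.

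The cost is one edited row in a blank table, plus a short definition if the stages stay. Blood loss in millilitres is already to be collected, so no new data are needed for the main change.
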